Reflow Medical Wingman Catheter Wing-IT Clinical Trial
RFM-CTO-13001
NCT03403426
Document Date: 03-OCT-2018

PROTOCOL SUMMARY

- Title:** A Non-Randomized Study Evaluating the Use of the ReFlow Medical **Wingman** Catheter to Cross Chronic Total Occlusions in Infringuinal Peripheral ArTeries (Wing-IT)
- Design:** Prospective, multi-center, non-randomized single-arm study of the Wingman Catheter to cross a single infringuinal peripheral chronic total occlusion (CTO). Safety and effectiveness will be evaluated during the index procedure through 30-day follow-up.
- Purpose:** To evaluate the safety and effectiveness of the ReFlow Medical Wingman Catheter used to cross *de novo* or restenotic infringuinal CTOs that cannot be crossed with a standard guidewire.
- Enrollment and Sites:** A maximum of 85 patients will be enrolled and treated with the investigational device at up to twelve (12) centers in North America and three (3) centers in Europe.
- Time Course:** Initial enrollment: Q1 2018
Last enrollment: Q1 2019
Last follow-up: Q1 2019
- Primary Efficacy and Safety Endpoints:** Primary Efficacy:
While using the Wingman device, successful CTO crossing is identified by successful guidewire placement in the distal true lumen confirmed by angiography with no clinically significant perforations.
Primary Safety:
No evidence of significant in-hospital or 30-day MAEs. No evidence of clinically significant perforation, clinically significant embolization or \geq Grade C dissection, after Wingman CTO crossing and prior to adjunctive interventions, confirmed by angiography. Components of the composite primary safety endpoint include:
- Major Adverse Events (MAEs) defined as death, unplanned target limb major amputation, and emergent target vessel revascularization.
 - Clinically significant perforation defined as all perforations requiring intervention (e.g., covered stent, bypass or other surgery)¹
 - Clinically significant embolization defined as those events that result in distal ischemia (e.g., occlusion of run-off vessel

resulting in pain or foot discoloration) and/or requires rescue intervention.

- Grade C Dissection or greater with a minimum of a dissection protruding outside the lumen of the vessel persisting after passage of the contrast material.¹

The components of the primary and secondary safety endpoints will be adjudicated by an independent CEC with angiographic elements assessed by an independent core laboratory.

Secondary Endpoints:

- 1) Lesion success, defined as attainment of <50% final residual stenosis of the target lesion using any percutaneous method.
- 2) Procedure success, defined as device success and the absence of in-hospital MAEs, clinically significant perforation, clinically significant embolization or Grade C or greater dissection not resolved by visual estimate.
- 3) Procedure safety, defined as any in-hospital AE or MAE following use of a therapeutic interventional device.
- 4) Evaluation of total procedural and fluoroscopic time and contrast volume.
- 5) Evaluation of procedure time associated with use of the investigational device.
- 6) Evaluation of utility of ancillary device in addition to investigational device.

Inclusion Criteria:

- 1) Patient is willing and able to provide informed consent.
- 2) Patient is willing and able to comply with the study protocol.
- 3) Patient is > 18 years old.
- 4) Patient has peripheral arterial disease requiring revascularization as evidenced by contrast, CT or MR angiography.
- 5) Patient has at least one but not more than two occluded infrainguinal arteries that are 99-100% stenosed and no flow is observed in the distal lesion except the flow from collateral circulation.
- 6) Target lesion(s) is ≥ 1 cm and ≤ 30 cm in length by visual estimate.
- 7) Target vessel is ≥ 2.0 mm in diameter.
- 8) Patient has Rutherford Classification of 2-5.
- 9) Lesion cannot be crossed by concurrent conventional guidewire.
- 10) Reconstitution of vessel at least 2cm above bifurcation/trifurcation.
- 11) Occlusion can be within previously implanted stent.

Exclusion Criteria:

- 1) Patient has a known sensitivity or allergy to contrast materials that cannot be adequately pre-treated.
- 2) Patient has a known sensitivity or allergy to all anti-platelet medications.
- 3) Patient is pregnant or lactating.
- 4) Patient has a co-existing disease or medical condition contraindicating percutaneous intervention.
- 5) Target lesion is in a bypass graft.

- 6) Patient has had a failed crossing attempt without an intervening intervention on the target limb within the past 14 days.
- 7) Patient has a planned surgical or interventional procedure within 30 days after the study procedure.

**Data Analysis
Center:**

Syntactx
[name]
[name]
[name]

Sponsor:

ReFlow Medical, Inc.
[name]
[name]

**Principal
Investigator:**

[name]

**Angiographic Core
Lab**

1 INTRODUCTION

The purpose of this clinical study is to evaluate the safety and effectiveness of the Wingman Catheter used to cross chronic total occlusions in infrainguinal peripheral arteries that failed crossing attempts with conventional guidewires. The Wingman Catheter is a percutaneous device that is designed to cross occlusions by using an extendable guide tip to dotter and penetrate through the plaque to create a channel. The Wingman Catheter is intended to be used in conjunction with standard endovascular devices and fluoroscopic guidance.

1.1 Design, Treatments and Visits

This is a prospective, multi-center, non-randomized single arm study of the Wingman Catheter to cross a single infrainguinal peripheral chronic total occlusion. This study will be conducted at up to twelve (12) investigational sites in North America and three (3) centers in Europe. Safety and efficacy will be evaluated during the index procedure through 30-day follow-up. The primary endpoint of this study is to assess crossing success with the Wingman device identified as confirmation of guidewire placement in the distal true lumen. The primary safety endpoint of this study will evaluate in-hospital and 30-day MAEs and clinically significant perforations. Secondary endpoints include the lesion (<50% final residual stenosis and grade 'C' or greater dissections created during the procedure that is not resolved by visual estimate) procedural success and safety rates; and the evaluation of procedural and fluoroscopic time/contrast volume. Patient follow-up will be recorded through 30 days post procedure.

1.2 Objectives

The Wingman device received FDA 510(k) clearance in August 2011 and February 2012 for use as a guidewire support device. Since then the device has been used in approximately two thousand five hundred (2500) commercial cases across centers within the US and globally to access discrete regions in the peripheral vasculature. This clinical study has been designed to assess the ability of the Wingman Catheter to facilitate crossing of CTOs in infrainguinal peripheral arteries. The Wingman's ability to access and facilitate crossing of CTOs is an important first step towards gaining access to treat these difficult lesions and securing guidewire positioning for therapeutic treatment.

1.3 Subject Population

Subjects with symptomatic peripheral arterial disease (PAD) requiring revascularization. A maximum of 85 subjects > 18 years of age, meeting all the following inclusion and none of the exclusion criteria, and who are willing to sign informed consent will be enrolled.

Patients must meet all the following inclusion criteria to be eligible for enrollment in this trial:

- 1) Patient is willing and able to provide informed consent.
- 2) Patient is willing and able to comply with the study protocol.
- 3) Patient is > 18 years old.
- 4) Patient has peripheral arterial disease requiring revascularization as evidenced by contrast, CT or MR angiography.

Statistical Analysis Plan

- 5) A maximum of 2 lesions can be treated per patient, as identified by the investigator, that have occluded infrainguinal arteries that are 99-100% stenosed and no flow is observed in the distal lesion except the flow from collateral circulation.
- 6) Target lesion is ≥ 1 cm and ≤ 30 cm in length by visual estimate.
- 7) Target vessel is ≥ 2.0 mm in diameter.
- 8) Patient has Rutherford Classification of 2-5.
- 9) Lesion cannot be crossed by concurrent conventional guidewire.
- 10) Reconstitution of vessel at least 2cm above bifurcation/trifurcation.
- 11) Occlusion can be within previously implanted stent.

Patients will be excluded from this trial if any of the following criteria are met:

- 1) Patient has a known sensitivity or allergy to contrast materials that cannot be adequately pre-treated.
- 2) Patient has a known sensitivity or allergy to all anti-platelet medications.
- 3) Patient is pregnant or lactating.
- 4) Patient has a co-existing disease or medical condition contraindicating percutaneous intervention.
- 5) Target lesion is in a bypass graft.
- 6) Patient has had a failed crossing attempt without an intervening intervention on the target limb within the past 14 days.
- 7) Patient has a planned surgical or interventional procedure within 30 days after the study procedure.

1.4 Sample Size Considerations

The exact binomial distribution is used for calculation of the sample size. The hypotheses and sample size calculations provided in the clinical study protocol are as follows.

The null and alternative hypotheses of the primary efficacy endpoint are:

$$H_0: \pi_{\text{Wingman_efficacy}} \leq \pi_{\text{PG_efficacy}} - \delta_{\text{efficacy}}$$

$$H_A: \pi_{\text{Wingman_efficacy}} > \pi_{\text{PG_efficacy}} - \delta_{\text{efficacy}}$$

where,

$$\pi_{\text{PG_efficacy}} = \text{PG success rate}$$

$$\pi_{\text{Wingman_efficacy}} = \text{Wingman device success rate}$$

Literature Review¹⁻¹¹ indicates that the average success rate of several CTO catheter device types is 83.2%. Using this rate as the historical control and using a non-inferiority margin (δ_{efficacy}) of 12.5% the hypotheses of the primary efficacy endpoint can be rewritten as:

$$H_0: \pi_{\text{Wingman_efficacy}} \leq 70.7\%$$

$$H_A: \pi_{\text{Wingman_efficacy}} > 70.7\%$$

The null and alternative hypotheses of the safety endpoint are:

$$H_0: \pi_{\text{Wingman_safety}} \geq \pi_{\text{PG_safety}} + \delta_{\text{safety}}$$

Statistical Analysis Plan

$$H_A: \pi_{\text{Wingman_safety}} < \pi_{\text{PG_safety}} + \delta_{\text{safety}}$$

where,

$$\pi_{\text{PG_safety}} = \text{PG major adverse event rate}$$

$$\pi_{\text{Wingman_safety}} = \text{Wingman device major adverse event rate}$$

Literature Review¹⁻¹¹ indicates that the average rate of major adverse events, perforations, grade C or higher dissections and embolizations is 5.0%. Using this rate as the historical control, and using a delta of non-inferiority margin (δ_{safety}) 8% for the safety endpoints, the hypotheses can be rewritten as:

$$H_0: \pi_{\text{Wingman_safety}} \geq 13.0\%$$

$$H_A: \pi_{\text{Wingman_safety}} < 13.0\%$$

Assume that the Wingman device has the same success rate and the major adverse event rate as the historical control and further assume that the one-sided type I error rates for the efficacy and safety endpoints are both 0.05. An effective sample size of 80 subjects is needed achieve a power of at least 80% for the efficacy and safety endpoints. To account for a loss of follow up rate of approximately 5%, total enrollment of 85 subjects is required.

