3.1 Intention-To-Treat Population

The subject is enrolled in the study once informed consent has been obtained. If the subject has provided informed consent but has not met one of the criteria for inclusion into the study, they will be considered a screen failure.

Modified Intention to Treat (mITT) Population: The modified intention to treat (mITT) population will include all consented subjects who are exposed to the investigational device. Subjects who give consent but are not exposed to the investigational device or do not undergo the procedure will not be included in this population. The primary study endpoints will be evaluated in the mITT population.

The study visit flow is as follows:

Activity	Visit 1 (Baseline Evaluation) ^a	Visit 2 ^a (Index Procedure through Discharge)	Visit 3 (Follow-Up Evaluation) ^e
Eligibility Screening	X		
Informed Consent	X		
History and Physical Examination of target limb ^f	X		
Vital Signs ^b	X	X	
Ankle-Brachial or Toe-Brachial and Rutherford Assessments	X	X	X
Medication History and Review	X		
Peripheral Arterial Disease/CTO Confirmation ^c	X		
Laboratory Tests ^d	X		
Interventional Procedure and Angiography		X	
Adverse Experience Assessment		X	X
Device Accountability		X	
Protocol Deviations	X	X	X

^a Visit 1 and Visit 2 study procedures may be conducted during one study visit, permitting that Visit 1 procedures have been performed within the past 90 days and are completed prior to the start of the interventional procedure. Urine pregnancy tests will also be conducted as necessary during the baseline evaluation per local requirements.

^b Blood pressure, heart rate, respiratory rate, and weight.

^c Confirmation of an occluded artery ≥ 2.0 mm in diameter requiring intervention based on contrast, CT or MR angiography.

^d As per pre-interventional catheterization laboratory standard procedures.

Statistical Analysis Plan

^e Visit will occur 30 days (+/- 7 days) post-interventional procedure.

^f Existence of gangrene, tissue deficit, blue toe syndrome or any evidence of acute ischemia in low limb.

Missing data will not be imputed. However, a tipping point sensitivity analysis on the primary endpoints will be done.

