4.2 Efficacy Analyses

Statistical Analysis Plan

Descriptive statistics of the primary efficacy endpoint (total number of CTOs, number and percentage of successful CTO crossings, one-sided 95% CI of the percentage) will be presented. The lower bound of the one-sided 95% CI will be compared to the performance goal of 70.7%.

Summary statistics will be presented for procedural and fluoroscopic time and contrast volume and other secondary endpoints. The summary will include number, mean, standard deviation, median, minimum, maximum, as well as the two-sided 95% CI of the mean and box plots for non-normally distributed data.

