4.3 Safety Analyses

Number and percentage of in-hospital and 30-day major adverse event and the one-sided 95% CI will be presented. The upper bound of the one-sided 95% CI will be compared to the performance goal of 13.0%.

Number and percentage of subjects having 30-day MAEs, device successes, lesion successes, procedure successes and subjects having clinically significant perforation, and the corresponding two-sided 95% CIs will be presented.

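### Safety power at the planned 80 subjects is 78.9%, not 80% or more, and it falls to 74.8% if all 85 are evaluable

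*SAP*

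**What the plan says.** SAP section 1.4 sets out the design calculation. On method it says "The exact binomial distribution is used for calculation of the sample size". The safety null rate is 13.0%, which is the 5.0% historical rate plus a margin of 8 points. The device is assumed to match the historical control, and each primary endpoint has a one-sided type I error of 0.05. One sentence then covers both endpoints: "An effective sample size of 80 subjects is needed achieve a power of at least 80% for the efficacy and safety endpoints".

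Enrolment is raised from there: "To account for a loss of follow up rate of approximately 5%, total enrollment of 85 subjects is required". Section 1.3 makes 85 a ceiling ("A maximum of 85 subjects > 18 years of age"), as does the Protocol Summary.

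On the analysis, section 3.1 says "The primary study endpoints will be evaluated in the mITT population", meaning consented subjects exposed to the device, so up to 85 can count. Section 4.3 gives the safety rule: "The upper bound of the one-sided 95% CI will be compared to the performance goal of 13.0"%. It names no interval method. The SAP states no safety power of its own, no limit on the number of events, and no power at 85.

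**The concern.** A single power statement covers two tests with different null rates, so each has to be checked separately. The safety test turns on a very small count. In that setting exact power moves in a sawtooth: it jumps when one more event becomes allowable and declines until the next jump. A sample size that suits efficacy can therefore fall on a declining stretch for safety, and adding subjects for expected losses can then lower safety power.

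Safety is a primary endpoint judged pass or fail against 13.0%. If the goal is missed, readers will ask how likely that was for an acceptable device, and the plan's answer is no more than 20%. If that figure is wrong, a missed goal would be read as stronger evidence against the device than it is.

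**Working it through.** **Inputs, all from SAP section 1.4:** exact binomial; one-sided alpha 0.05; safety goal 5.0% + 8% = 13.0%; true safety rate 5.0%; efficacy goal 83.2% − 12.5% = 70.7%; true efficacy rate 83.2%; 80 effective subjects; about 5% loss.

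**What reproduces**

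- Enrolment: 80 / 0.95 = 84.2, rounded up to 85.
- Efficacy at n = 80, one outcome per subject: the smallest r with P(X ≥ r | 80, 0.707) ≤ 0.05 is r = 64 (actual alpha 0.0405). Power = P(X ≥ 64 | 80, 0.832) = 82.2%.

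**Safety rule and power**

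The limit c is the largest k with P(X ≤ k | n, 0.13) ≤ 0.05. Power = P(X ≤ c | n, 0.05).

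At n = 80:

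- P(X ≤ 5 | 80, 0.13) = 0.0426, so 5 events pass.
- P(X ≤ 6 | 80, 0.13) = 0.0911, so 6 events fail.
- The exact (Clopper-Pearson) one-sided 95% upper bounds agree: 12.69% for 5/80 and 14.27% for 6/80.
- Power = P(X ≤ 5 | 80, 0.05) = 0.7892. The shortfall is 80.0 − 78.9 = 1.1 points, and the chance of failing is 100 − 78.9 = 21.1%.

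At n = 85:

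- P(X ≤ 5 | 85, 0.13) = 0.0280 and P(X ≤ 6 | 85, 0.13) = 0.0632, so the limit is still 5.
- Upper bounds: 11.97% for 5/85 and 13.46% for 6/85.
- Power = P(X ≤ 5 | 85, 0.05) = 0.7482. The shortfall is 5.2 points, and the chance of failing is 25.2%.

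| n | Events allowed | Actual alpha (safety) | Safety power | Efficacy rule | Efficacy power |
|---|---|---|---|---|---|
| 79 | 5 | 0.046 | 79.7% | ≥63 | 83.5% |
| 80 | 5 | 0.043 | 78.9% | ≥64 | 82.2% |
| 81 | 5 | 0.039 | 78.1% | ≥65 | 80.8% |
| 82 | 5 | 0.036 | 77.3% | ≥66 | 79.3% |
| 83 | 5 | 0.033 | 76.5% | ≥66 | 85.2% |
| 84 | 5 | 0.031 | 75.7% | ≥67 | 83.9% |
| 85 | 5 | 0.028 | 74.8% | ≥68 | 82.6% |
| 88 | 5 | 0.022 | 72.3% | ≥70 | 85.5% |
| 89 | 6 | 0.047 | 84.2% | ≥71 | 84.3% |

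A sixth event becomes allowable only at n = 89, which is the first size with 80% safety power.

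**How much safer the device would have to be.** Solving P(X ≤ 5 | n, p) = 0.80 gives p = 4.91% at n = 80 and p = 4.62% at n = 85, against the assumed 5.0%.

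**Whether another method explains the stated figure (safety, n = 80).** A normal approximation with null variance gives 77.2%, and with continuity correction 68.7%. An arcsine approximation gives 82.1%, and a normal approximation with alternative variance 94.9%. The last two exceed 80%, but neither is the exact method the SAP names.

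**Whether another interval in section 4.3 would help**

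- Wilson: the limit stays at 5 events from 80 to 85.
- Wald: 6 events allowed. Power is 89.5% at 80 and 86.7% at 85, but actual alpha is 0.091 and 0.063.
- Mid-p or Jeffreys: 5 events at 80 to 83 and 6 at 84 and 85. For 6/85 the mid-p value is 0.0456 and the Jeffreys bound 12.72%. Power at 85 is then 86.7%, with actual alpha 0.063.

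**The case against.** The best counter-argument is that the only stated figure shown to be wrong is off by 1.1 points. The 5.0% rate is an average over published reports, and a true rate of 4.91% would restore 80% at n = 80; no planning input is known that precisely. The SAP gives no power at 85, so 74.8% contradicts nothing it says, and it arises only if the expected 5% loss does not occur. It also depends on reading the unnamed interval in section 4.3 as exact, since mid-p or Jeffreys would allow a sixth event at 85. Finally, the SAP is dated May 2019, after the protocol's planned last follow-up in the first quarter of 2019. On that schedule a corrected power figure cannot alter the trial.

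Much of this stands as a limit on importance. The error at 80 is small, the figure at 85 is a consequence of the design and not a misquoted number, and the decline in power simply reflects a stricter test as actual alpha falls from 0.043 to 0.028.

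It does not remove the finding. The text states a floor, and 78.9% is below it on the plan's own inputs. The shortfall is also not confined to one sample size: no n from 80 to the cap of 85 reaches 80%. The intervals that allow a sixth event do so only with actual alpha above the 0.05 that section 1.4 sets. The figure still matters for reporting, because a missed safety goal would be read against it.

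**Conclusion.** The safety part of the power statement is wrong as written. Exact power is 78.9% at the planned 80 subjects and declines with each further evaluable subject to 74.8% at 85. The shortfall is 1.1 points in the planning case and 5.2 points with no losses. Reaching 80% would take 89 evaluable subjects.

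This rests on the SAP's own rates and alpha, on one safety outcome per subject, and on carrying the exact method of section 1.4 into the comparison in section 4.3. The risk of a false pass is not raised.

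The efficacy statement is correct at 80 and at 85, though power dips to 79.3% at n = 82. That check counts one outcome per subject, whereas section 4.2 tabulates by lesion ("total number of CTOs, number and percentage of successful CTO crossings") and section 1.3 permits two lesions per patient.

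This should be corrected, but it is a misstatement of power and not a fault in the decision rule.

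**What to change.** Keep the sample size, the 13.0% goal, alpha and the decision rule. In SAP section 1.4, withdraw the 80% floor for safety and replace the joint sentence with wording such as:

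> With 80 to 85 evaluable subjects, exact power for safety is about 79% at 80, falling to 75% at 85 (at most 5 events allowed). Exact power for efficacy, counted per subject, is about 82% at 80 and 83% at 85 (range 79% to 85%).

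Section 1.4 attributes its figures to the protocol ("The hypotheses and sample size calculations provided in the clinical study protocol are as follows"). The protocol's sample-size section is not in the supplied text, so it should be checked and corrected if it carries the same statement.

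A useful addition, not essential to the correction, is to name the exact (Clopper-Pearson) bound in section 4.3, so that the analysis is tied to the 5-event limit.

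The cost is a few lines of text and a slightly less favourable stated safety power. No further patients are needed.

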1.5 Randomization

This is a non-randomized study.

2 ENDPOINT DEFINITIONS

2.1 Primary Efficacy Endpoint

Successful CTO Crossing – While using the Wingman device, successful CTO crossing is identified by successful guidewire placement in the distal true lumen confirmed by angiography with no clinically significant perforations.

All of the angiographic films obtained from this study will be reviewed by an independent core lab. Information from their angiographic review will be recorded on CRFs and tabulated for endpoint analysis. Angiographic review will include assessments of: lesions lengths, occlusion lengths, reference vessel diameter, calcification severity, successful CTO crossing, perforation and dissection.

In the event angiographic films are unavailable for assessment by the core lab, site-reported visual assessments will be used for analysis.

2.2 Secondary Efficacy Endpoints

Statistical Analysis Plan

- Lesion success, defined as attainment of <50% final residual stenosis of the target lesion using any percutaneous method.
- Procedure success, defined as device success and the absence of in-hospital MAEs, clinically significant perforation, clinically significant embolization or Grade C or greater dissection not resolved by visual estimate.
- Evaluation of total procedural and fluoroscopic time and contrast volume.
- Evaluation of procedure time associated with use of the investigational device.
- Evaluation of utility of ancillary device in addition to investigational device.

The angiographic elements of secondary efficacy endpoints will be assessed by an independent core laboratory and the MAE elements adjudicated by an independent CEC. In the event angiographic films are unavailable for assessment by the core lab, site-reported visual assessment will be used for analysis.

